5.4 Timing of the DFS and OS Interim and Final Analyses

This study includes two interim looks and one final look. The first interim look of this study will include the DFS interim analysis (DFS IA) and the first OS interim analysis (OS IA1). The second interim look of this study will include DFS final analysis (DFS FA) and the second OS interim analysis (OS IA2). The final look of this study will be OS final analysis (OS FA).

Timing of the Interim and Final DFS Analyses

Considering the potential plateau of the DFS curve after 3 years,⁴ the study is designed with 1 interim DFS analysis when at least 85% of all 440 DFS events (374 DFS events) are observed. Based on the current assumptions, it is projected to occur approximately 12 months after the last

patient being randomized. The final DFS analysis will be triggered when at least 440 DFS events have been observed. The final DFS analysis is projected to occur approximately 22 months after the last patient being randomized. The stopping boundaries at the interim and final DFS analyses will be derived based on the exact number of DFS events observed using Lan-DeMets alpha spending function with O’Brien-Fleming boundaries.

Timing of the Interim and Final OS Analyses

Based on the current design, the first interim OS analysis is planned at the time of the DFS interim analysis, and the second interim OS analysis is planned at the time of the DFS final analysis. It is expected to have approximately 65% and 80% of OS events at the time of the interim DFS and final DFS analysis respectively. This formal comparison of OS will allow for early stopping of the study for superiority. The stopping boundaries at the interim and final OS analyses will be derived based on the exact number of deaths observed using Lan-DeMets alpha spending function with O’Brien-Fleming boundaries.

The final OS analysis will be triggered when at least 460 OS events have been observed and is projected to occur approximately 41 months after the last patient being randomized.

The timing and power of the interim and final DFS and OS analyses are summarized in Table 5.1-3.

The statistical software East version 6.3 (Cytel, Inc 2010) was used for study design calculations.

Table 5.1-3: Timing and Power of Interim and Final DFS and OS Analyses

	DFS	OS
Interim Analysis (IA) for DFS/IA 1 for OS		
Projected time from 1st patient randomized	48 months	48 months
Number of events	374 (85% of all DFS events)	299 (65% of all OS events) ^a
Significance level	0.03	0.01
Probability of crossing boundary	81%	45%
Final Analysis (FA) for DFS/IA 2 for OS		
Projected time from 1st patient randomized	58 months	58 months
Number of events	440	368 (80% of all events) ^b
Significance level	0.042	0.022
Cumulative Probability of crossing boundary	91%	70%

Table 5.1-3: Timing and Power of Interim and Final DFS and OS Analyses

	DFS	OS
FA for OS		
Projected time from 1st patient randomized	NA	77 months
Number of events		460
Significance level		0.042
Cumulative Probability of crossing boundary		90%

^a IA 1 for OS is at the time of DFS interim analysis. The actual number of OS events may be different.

^b IA 2 for OS is at the time of DFS final analysis. The actual number of OS events may be different.

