		
• Updated the abbreviations list• Revised the Appendix 2 (Safety Management Algorithms)• Added Appendix 3 (Women of Childbearing Potential and Methods of Contraception)• Other minor changes incorporated into this amendment include changes in document names, study materials that will be provided to sites, removal of duplicate statements, revisions to section numbering, and formatting changes
Administrative Letter 01	10-Feb-2016	
• Fixed the protocol title• Removed the reference to neck as an anatomical imaging area for the CT/MRI scan• Updated a section number
Original Protocol	06-Jan-2016	Not applicable

OVERALL RATIONALE FOR REVISED PROTOCOL 04

The rationale for the change to the overall survival (OS) final analysis (FA) trigger includes factors observed during the conduct of the trial. The actual OS event accrual in the study has been much slower than projected. Initial projections for the OS FA estimated [REDACTED]

Blinded

OS event tracking commenced in 2021 after the first planned interim analysis was completed. While Bristol-Myers Squibb (BMS) remains blinded to the number of OS events by treatment arm, the overall accrual of events has slowed significantly year over year, since tracking began. [REDACTED]

The treatment landscape has changed markedly since the study was designed. Patients who experience recurrence after adjuvant therapy have increased treatment options and can receive subsequent therapy with immune checkpoint inhibitors (ICI) or a combination of immune checkpoint inhibitors with chemotherapy. A portion of patients may also be cured with treatment. Increased treatment options may reduce disease mortality, therefore impacting the OS event rate.

Protocol Amendment 04 adds the option to conduct a time-driven analysis. [REDACTED]

SUMMARY OF KEY CHANGES FOR REVISED PROTOCOL 04		
Section Number & Title	Description of Change	Brief Rationale
Title Page	Updated European Union (EU) Trial Number. Updated Medical Monitor address.	Administrative update.
Synopsis Statistical Considerations	Added the option to conduct overall survival (OS) final analysis (FA) [REDACTED]	Refer to the overall rationale for revised protocol.
Section 2.1: Good Clinical Practice Section 6.1.1: Serious Adverse Event Collection and Reporting	Replaced Directive 2001/20/EC with European Regulation 536/2014.	To update the legal framework of the trial after transition to EU-CTR.

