5.3 Sample Size and Power

According to the assumptions for DFS described in Sections 5.1 and 5.2, the study will require approximately 760 subjects to be randomized at a 2:1 ratio to nivolumab and placebo and observations of at least 440 DFS events in order to achieve approximately 91% power to detect an average HR of 0.72 at a 2-sided alpha of 0.05.

The sample-size determination accounts for 1 DFS interim analysis. Details of the DFS analysis timing are provided in Section 5.4.

It is estimated that these 760 subjects will be accrued and randomized within approximately 36 months from the first-patient first-visit (FPFV).

Overall survival will be tested following the overall hierarchical testing procedure¹¹ upon demonstration of superiority in DFS at either interim or final analyses for all randomized subjects.

With the sample size of 760, it is required to observe at least 460 OS events at the final OS analysis in order to achieve approximately 90% power to detect an average HR of 0.73 at a 2-sided alpha of 0.05. The power of the OS final analysis accounts for 2 OS interim analyses that occur at the same time as the DFS interim and DFS final analyses, respectively. Details of the OS analysis timing are provided in Section 5.4.

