5.5 Potential Adjustment of Analysis Timing for DFS and OS

As discussed in the [Section 5.1](#) of this SAP, there was no historical trial with the exact same population studied in this trial. As such, the assumptions made for the DFS and OS in the control arm might be very different from the actual rates. Since the events rates will impact the data maturity and timing of DFS and OS analyses, BMS will conduct periodic monitoring of the DFS and OS events rates in a pooled, blinded fashion under the assumed HR of DFS and OS once a majority of the subjects are randomized. Should such monitoring suggests a big variability of the assumptions made for DFS and OS in the control arm, the impact on the data maturity and timing of analyses for DFS and OS will be evaluated and the trigger for the timing of the DFS and OS analyses may be adjusted accordingly.

If the blinded monitoring suggested a modification of the trigger of the interim looks, this document will be used to document such changes prior to the first interim look of this study.

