If the analysis is performed with the event number exactly the same as those specified in [Table 5.1-3](#), the alpha allocation for DFS and OS is as specified in Table 7.5.1-1. For example if the timing of the interim DFS analysis is performed exactly at 85% of all 440 DFS events (374 DFS events), the boundary in terms of statistical significance for declaring superiority would be $\alpha_{1,1} = 0.03$. The boundary for declaring superiority in terms of statistical significance for the final DFS analysis after 440 DFS events would be 0.042. The significance levels for the final DFS analysis will be adjusted according to the actual alpha spent at the interim analysis and the actual number of DFS events at the interim and final analyses.

The significance levels for the final OS analysis will be adjusted according to the actual alpha spent at interim analysis 1 and interim analysis 2 and the actual number of OS events at OS interim analysis 1, interim analysis 2, and final analysis.

Table 7.5.1-1: Alpha Allocation if the Analysis is Performed with the Event Number Exactly the Same as Specified.

Analysis Timing	DFS		OS	
	Event Number (%of all events)	Alpha	Event Number (%)	Alpha
IA DFS & IA1 OS	374 (85%)	$\alpha_{1,1} = 0.03$	299 (65%)	$\alpha_{2,1} = 0.01$
FA DFS & IA2 OS	440	$\alpha_{1,2} = 0.042$	368 (80%)	$\alpha_{2,2} = 0.022$
FA OS	NA	NA	460	$\alpha_{2,3} = 0.042$

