9 DOCUMENT HISTORY

Table 9-1: Document History

Version Number	Author(s)	Description
1.0 Apr 25, 2017		Original Issue based on revised protocol 01 dated Aug 24, 2016

Table 9-1: Document History

[figure not shown]
[figure not shown]

2.0 Oct 24, 2019
		
Based on revised protocol 03 dated June 06, 2019. The following changes are made in the SAP amendment to reflect the protocol amendment of having DFS as the primary endpoint, and OS as the secondary endpoint.  .
 
 • Objectives and endpoints to keep DFS as the sole primary endpoint and change OS to the secondary endpoint • Sample size and power • Schedule of analyses • The method to maintain blinding of OS if not positive at two interim looks of the studyThe method for alpha spending between IA and FA for DFS and OS PFS2 definition and analyses 
The SAP amendment also incorporates the IO core SAP.

3.0 May 4, 2020
		
Minor updates from SAP version 2.0 to add sensitivity analyses in Section 7.5.2.1 and other minor edits. Details are summarized below.
 
 • • Remove dose reduction in Section 7.6.4 as it is not applicable in this study. • Include in 7.5.2.2 Consistency of Treatment Effect in Subsets, Pathologic tumor status (ypT0, ypT1/ypT2, ypT3/ypT4, unknown) • Remove cumulative plot of baseline PD-L1 expression in section 7.8 as it is not very informative. • Remove the log-rank test and keep the Cox model for the subgroup analysis by PD-L1 status in section 7.8. • Add "c) no on-study disease assessment but death with prior subsequent therapy or second primary cancer" for censored on randomization date in section 7.5.2

4.0 Sept 30, 2020
		
Minor format update on hyperlinks, references, and page numbers. Correction of the relative dose intensity formula in Table 7.4-1 Administration of study therapy: definition of parameters.

Table 9-1: Document History

--	--	--

APPENDIX 1 TIME-TO ONSET AND TIME-TO RESOLUTION DEFINITION AND CONVENTIONS FOR SELECT ADVERSE EVENTS, IMMUNE-MEDIATED ADVERSE EVENTS AND EVENTS OF SPECIAL INTEREST

Time-to onset definition

Time-to onset of AE (any grade) for a specific category is defined as the time between the day of the first dose of study treatment and the onset date of the earliest AE (of any grade) in this category.

The time-to onset of AE (grade 3-5) for a specific category is defined similarly with an onset date corresponding to a grade 3-5 AE.

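### Does the SAP need changing because it lacks the protocol's time-driven final OS look, quotes OS power without the DFS gate, and prints 0.042 as the final DFS level?

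*SAP*

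**What the plan says.** SAP 5.4 triggers the last OS look on deaths alone: "The final OS analysis will be triggered when at least 460 OS events have been observed". SAP 9 (Document History) shows that v2.0 was "Based on revised protocol 03 dated June 06, 2019"; v3.0 and v4.0 (30 September 2020) made minor updates.

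The Protocol's rationale for Revised Protocol 04 (26 April 2024) says "The actual OS event accrual in the study has been much slower than projected" and that "Protocol Amendment 04 adds the option to conduct a time-driven analysis". The details, in Protocol 8.1.4 and 8.1.5, are redacted.

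SAP 5.5 says that, after blinded monitoring of pooled event rates, "the trigger for the timing of the DFS and OS analyses may be adjusted accordingly". It adds: "If the blinded monitoring suggested a modification of the trigger of the interim looks, this document will be used to document such changes", and limits this to the time before the first interim look.

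On alpha, SAP 7.5.1 passes the full alpha to OS once DFS is rejected. It then says: "The significance levels for the final OS analysis will be adjusted according to the actual alpha spent" at both OS interims and to the actual deaths at all three looks.

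On power, SAP 5.3 states that OS is tested only after DFS superiority. It then gives 460 deaths "in order to achieve approximately 90% power to detect an average HR of 0.73 at a 2-sided alpha of 0.05" and says this power accounts for the two OS interims. Table 5.1-3 prints cumulative OS probabilities of 45%, 70% and 90%. It prints levels of 0.03 and 0.042 for DFS, and 0.01, 0.022 and 0.042 for OS.

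**The concern.** Three things catch the eye.

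1. Protocol and SAP differ on what may trigger the final OS analysis. The sentence in SAP 5.5 on recording trigger changes reaches only the interim looks. If the last look comes below 460 deaths, one could treat it as the end of the trial and spend everything left, or treat it as a fraction of 460 and spend only that share. One p-value could then pass under one reading and fail under the other. OS is the only secondary endpoint under family-wise control.
2. The 90% could be mistaken for the probability that the trial claims an OS benefit. It leaves out the chance that DFS fails and OS is never tested.
3. Taken literally as boundaries, 0.03 and 0.042 spend slightly more than 0.05 on DFS.

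**Working it through.** **Inputs.** Two-sided alpha 0.05; DFS looks at 374 and 440 events; OS looks at 299, 368 and 460 deaths; Lan-DeMets spending of O'Brien-Fleming type (SAP 5.3, 5.4, Table 5.1-3). Cumulative two-sided alpha at information fraction t is 4[1 − Φ(2.2414/√t)], where 2.2414 is the upper 0.0125 normal point. Each later nominal level is solved so that the total crossing probability equals the cumulative spend, with correlation √(t₁/t₂) between looks.

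**Printed levels.**

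| Look | Unrounded chain | Printed interim level carried forward | SAP prints |
|---|---|---|---|
| DFS interim (t = 0.85) | 0.0301 | 0.03 | 0.03 |
| DFS final | 0.0414 | 0.0415 | 0.042 |
| OS interim 1 (t = 0.65) | 0.0109 | 0.01 | 0.01 |
| OS interim 2 (t = 0.80) | 0.0212 | 0.0217 | 0.022 |
| OS final | 0.0422 | 0.0423 | 0.042 |

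Carrying the printed interim level forward reproduces every printed value. The unrounded chain would print 0.041 for the DFS final look, and 0.011 and 0.021 for the OS interims, so it is not the convention the table follows. Using 0.03 and 0.042 literally spends 0.0504, an excess of 0.0004; 0.03 and 0.041 spends 0.0496. SAP 5.4 and 7.5.1 derive the operative boundaries from exact event counts, so neither printed value is used in a test.

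**Power figures.** Simulation used the hazards in SAP Tables 5.1-1 and 5.1-2, 760 subjects allocated 2:1, uniform accrual over 36 months, no dropout and an unstratified log-rank test (the last three are assumptions). Without the DFS gate, OS power is about 44–45%, 70–71% and 90%, and DFS power about 81% and 91–92%. The printed 45/70/90% and 81/91% are therefore reproduced.

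With the gate, the printed 91% and 90% alone bound the probability of an OS claim:
- lower bound: 0.91 + 0.90 − 1 = 0.81;
- upper bound: min(0.91, 0.90) = 0.90;
- if independent: 0.91 × 0.90 = 0.82.

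Models in which death cannot precede the DFS event give 86–89%. Where the figure falls depends on an assumed DFS–OS dependence, for which the documents give no number.

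**Final OS look below 460 deaths.** The death counts are assumed, with interims at the planned 299 and 368. Power uses the Schoenfeld drift for a constant HR of 0.73 with 2:1 allocation; on that basis it is 88% at 460 deaths.

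| Deaths | Level, all remaining alpha | Level, capped at deaths/460 | Total spent if capped | Power, all / capped |
|---|---|---|---|---|
| 380 | 0.048 | 0.020 | 0.027 | 82% / 74% |
| 400 | 0.047 | 0.025 | 0.032 | 84% / 78% |
| 420 | 0.045 | 0.030 | 0.038 | 86% / 82% |
| 440 | 0.043 | 0.036 | 0.044 | 87% / 85% |

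The first reading spends exactly 0.05. The second spends less and leaves the rest unused. Neither exceeds 0.05, provided the cut is not chosen with knowledge of the OS difference. The Protocol's rationale says the sponsor remains blinded to OS events by arm, which supports that condition.

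**Which reading the SAP supports.** SAP 7.5.1 gives OS the full alpha and recalculates the final level from alpha already spent and actual deaths, naming the final analysis itself. In ordinary group-sequential practice the last look uses whatever alpha remains. Nothing in either document says that part of the 0.05 would be left unspent.

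**The case for a change.** The strongest opposing case concerns the alpha rule. Protocol 8.4.2.1 leaves the details of type I error protection to the SAP. SAP 5.4 expresses OS information as a percentage of 460, so a capped reading can be constructed. The sentence in SAP 7.5.1 does not say in terms that a short final look has information fraction 1. At 400 deaths any p-value between 0.025 and 0.047 would change the verdict, and settling the rule after unblinding would invite challenge.

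Part of this stands. The supplied SAP does not mention the time-driven option, and the spending rule would be better written down before the cut. But a 2020 SAP cannot carry a 2024 amendment, and a later version may exist. Protocol 8.1.4 and 8.1.5 are redacted. Protocol Appendix 5 describes 8.1.5 as covering how analysis timing can move under strong type I control, with the SAP recording such changes. The interim-look sections listed in the SAP's table of contents (7.5.5 to 7.5.7) cannot be read either. What remains is a sentence stating what an analyst would do anyway.

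For the power figures, a label such as ungated would do no harm. The gate is stated immediately before the 90%, though, and OS is never tested unless DFS has already been rejected, so a pre-gate design probability has no bearing on that test.

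**Conclusion.** No change to the plan follows. The trigger mismatch is real but reflects document dates, and the alpha rule is a gap that standard practice and SAP 7.5.1 fill in one direction: the last OS look spends what remains. The alternative would cost about 8 points of power at 380 deaths (82% against 74%) and about 1 to 2 points at 440, but nothing in the documents calls for it. These sizes assume a final count below 460, interims at exactly 299 and 368 deaths, and an average HR of 0.73. The actual interim counts may differ, and slower mortality would alter follow-up and possibly the average HR.

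The 45/70/90% figures are reproduced as OS-only crossing probabilities. A gated figure lies between 81% and 90%, depending on an assumption the documents do not supply, and would change no decision. The 0.042 is 0.0415 rounded, and the boundary actually applied is recomputed from observed events.

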5.5 Potential Adjustment of Analysis Timing for DFS and OS

As discussed in the [Section 5.1](#) of this SAP, there was no historical trial with the exact same population studied in this trial. As such, the assumptions made for the DFS and OS in the control arm might be very different from the actual rates. Since the events rates will impact the data maturity and timing of DFS and OS analyses, BMS will conduct periodic monitoring of the DFS and OS events rates in a pooled, blinded fashion under the assumed HR of DFS and OS once a majority of the subjects are randomized. Should such monitoring suggests a big variability of the assumptions made for DFS and OS in the control arm, the impact on the data maturity and timing of analyses for DFS and OS will be evaluated and the trigger for the timing of the DFS and OS analyses may be adjusted accordingly.

If the blinded monitoring suggested a modification of the trigger of the interim looks, this document will be used to document such changes prior to the first interim look of this study.

6 STUDY PERIODS, TREATMENT REGIMENS AND POPULATIONS FOR ANALYSES

6.1 Study Periods

- Baseline period:
 - ◆ Baseline evaluations or pre-treatment events will be defined as evaluations or events that occur before the date and time of the first dose of study treatment. Evaluations (laboratory tests, vital signs, and biomarkers) on the same date and time of the first dose of study treatment will be considered as baseline evaluations. Events (AEs) on the same date and time of the first dose of study treatment will not be considered as pre-treatment events.

- In cases where the time (onset time of event or evaluation time and dosing time) is missing or not collected, the following definitions will apply:
 - ◆ Pre-treatment AEs will be defined as AEs with an onset date prior to but not including the day of the first dose of study treatment;
 - ◆ Baseline evaluations (laboratory tests, vital signs, and biomarkers) will be defined as evaluations with a date (and time if collected) on or prior to the date of first dose of study treatment.
- If there are multiple valid observations in the baseline period, then the latest non missing observation will be used as the baseline in the analyses. If multiple observations exist on the latest collection date (and time if collected), the record with the latest data entry date and time will be used. If multiple observations exist on the latest collection date (and time if collected) and data entry date and time, then the first observation is used as baseline, unless otherwise specified.
 - ◆ For PD-L1, non-missing is identified as those with quantifiable test result. After applying the rule above, if there are no records with a quantifiable test result, then select those with indeterminate result (“INDETERMINATE”). If there are no records with indeterminate test result, then select those with unavailable result (“NOT EVALUABLE”). If there are no records with unavailable test result, then select those which are not reported or not available result (all other records).
 - ◆ For Anti-Drug Antibody (ADA), the baseline record of nivolumab immunoglobulin (IMG) evaluation must be less than the date and time of the first nivolumab dose date and time.
- Post baseline period:
 - On-treatment AEs will be defined as AEs with an onset date and time on or after the date and time of the first dose of study treatment (or with an onset date on or after the day of first dose of study treatment if time is not collected or is missing). For subjects who are off study treatment, AEs will be included if event occurred within a safety window of 30 days (or 100 days depending on the analysis) after the last dose of study treatment. No “subtracting rule” will be applied when an AE occurs both pre-treatment and post-treatment with the same preferred term and grade.
 - On-treatment evaluations (laboratory tests, and vital signs) will be defined as evaluations taken after the day (and time, if collected and not missing) of first dose of study treatment. For subjects who are off study treatment, evaluations should be within a safety window of 30 days (or 100 days depending on the analysis) after the last dose of study treatment.

